Project Title: A Pilot Study Investigating the nCAP Signal Relief Patch in Subjects

Undergoing Primary Hip or Knee Replacement Surgery: A Prospective, Randomized,

Open Label Trial

IRB: STUDY22010018

NCT: 05252858

Date of Approval: 08/10/2022

Statement of Problem

The current opioid epidemic has led to a renewed interest in exploring nonpharmacological techniques to treat post-operative pain. Opioids are also not the drug of choice for the treatment of perioperative pain because their administration is associated with adverse effects, including post-operative nausea and vomiting, respiratory depression, immunosuppression, constipation, and opioid use disorder and the risk of opioid overdose and death. In the United States, over \$600 billion is spent every year on opioid addiction, including \$79 billion related to opioid addiction following surgery. Despite many initiatives to decrease the use of opiates in the preoperative setting, opioids continue to be regularly prescribed before, during, and after surgery. Although the risk of opioid addiction following surgery is recognized, the percentage of patients becoming addicted to opioids following surgery is not well understood. Although guidelines have been published regarding the use of opioids, it is established that opioids are still overused. Therefore, in order to combat this growing health crisis at the ground level, it is incumbent upon the medical community to explore alternative methods to the use of opioids and apply these approaches to surgical population. This is especially important in the context of COVID-19 because it is clear that we have been experiencing an increase in death related to opioid overdose.

Evidence supports the concept that the human body is "electric." This property is routinely used to monitor organ function such as the heart, the brain, and more. In the case of local trauma and pain, it is established that pain is the result of local inflammation, a local decrease in pH and therefore an accumulation of negative charges. In this respect the nCAP Nano patch is a patch charged negatively. Therefore, when applied at the site of the pain, the

patch redistributes the negative charges at the local level and this redistribution away from the local site has an anti-inflammatory and an analgesic effect.

Specific Aims

- 1. The primary endpoint will be to prospectively investigate the efficacy of the nCAP Signal Relief Patch in reducing perioperative opioid requirement (up to 72 hours post-op) in opioid-naïve patients undergoing primary unilateral total hip or knee replacement surgery. Opioid requirement will be estimated following the placement of the patch.
- 2. The secondary endpoint will include the effects of nCAP Signal Relief Patch after the placement on postoperative pain, functional recovery, time to discharge from the hospital, and opioid related complications, such as, PONV, itching, sleep disorders, respiratory depression, and urinary retention.

Study Design

The proposed pilot study will be conducted as a single-center prospective, randomized, open label trial at the University of Pittsburgh Medical Center (UPMC) Shadyside Hospital.

Institutional review board approval will be obtained before eligible patients are recruited and consented. The trial will be registered at www.clinicaltrial.gov before beginning recruitment.

The efficacy of this device will be established by comparing postoperative opioid requirement to maintain pain scores \leq 4 using a Numerical Rating Scale (NRS). Accordingly, pain will be treated according to the following protocol: pain scores \leq 4, non-opioid analysics, pain scores between 4 and 6 oxycodone 5 mg q 4 hrs and \geq 7, oxycodone 10 mg, Hydromorphone IV 0.2-0.5 mg q 3 hr. Data collected following the placement in the treatment group (Standard of Care ERAS protocol + nCAP Signal Relief Patch) will be compared to the data obtained in the control group (Standard of Care ERAS protocol).

Recruitment

Potential subjects may be given a recruitment flyer (attached) in the office of surgeons Drs.

[name], [name], or [name]. The potential subjects who receive a flyer will then have the option of contacting the study team to discuss the study further, or, if they express interest in participating in the surgeon's office, their name will be given to the study team from the surgeon's office staff.

Potential subjects may also be identified by the study team who has normal access to the Operating Room Schedule and electronic medical records. If a subject is deemed eligible via inclusion/exclusion criteria, a study team member will approach them the morning of their scheduled surgery and discuss the study with them at length and answer any questions they may have. If a potential subject is willing to sign consent, then a physician investigator will be available to review the consent, risks and benefits of participation, and obtain informed consent.

If our research team is contacted prior to the day of surgery, or if we reach out based upon the list of interested potential subjects, study team will discuss the study at length over the phone and answer any questions the potential subjects may have. Subjects interested in participating will be emailed the currently approved informed consent form to review. They will be given the option to sign consent electronically for convenience via REDCap or they can sign consent form on the day of surgery in the pre-operative holding area.

The subject will be approached as soon as they arrive to the hospital (at least 2-3 hours before their surgery) and will be given adequate time to consider the consent and ask questions. The patient will be urged to take as long as necessary to decide whether or not to participate. If the

subject feels they do not have enough time to make a decision, they will not be enrolled in the trial.

All questions will be addressed and it will be made clear that the patient may withdraw from the study at any time. Investigator physician will sign the informed consent with the patient prior to beginning of any study procedures.

Randomization Process

Participating patients will be randomized by computer-generated random numbers to either the control group (standard of care ERAS protocol) or intervention group (nCAP Signal Relief Patch group+ ERAS protocol).

Inclusion Criteria:

- Over 18 years of age
- Scheduled for elective primary unilateral hip or knee replacement surgery

Exclusion Criteria:

- Active clinical depression, anxiety, or catastrophizing
- Raw score equal to or greater than 19 on the PROMIS Anxiety 8a Adult v1.0
- Active alcoholism or drug abuse
- Severe chronic pain condition that requires daily preoperative opioid dependence
- Total surgery revision, bilateral hip replacement, multiple surgeries

Treatment Groups

Each subject will undergo surgery and anesthesia using the approved ERAS protocol.

Control Arm (n=30): Control group will receive approved ERAS multimodal anesthesia protocol (standard of care).

Interventional Arm (n=30): Intervention group will receive approved ERAS multimodal anesthesia protocol plus an nCAP Signal Relief Patch.

Data Collection and Outcome Measures

After signing an informed consent, subjects will complete the PROMIS Emotional Distress – Anxiety – Short Form 8a before completing any other questionnaires. Subjects who have a raw score <19 will be enrolled in the study. Any subject who scores \ge 19 will be considered a screen failure and excluded from the study.

Once the subject is enrolled, they will be asked to complete the Pain Catastrophizing Scale (PCS), the PROMIS® Emotional Distress-Depression - Short Form 8a, and the PROMIS® Item Bank v1.0 – Sleep- Disturbance – Short Form 8a prior to surgery. The subject will also conduct a baseline functionality test to assess mobility and strength in their leg. The functional recovery will be assessed by determining the patient ability to walk 100 feet, go up 5 steps and raise their leg on the day of surgery. Scores can be 0 (no ability to raise the leg), 1 (some ability to raise the leg), and 2 (complete ability to raise the leg).

Once these assessments are completed, subjects will be equally randomized to the intervention group (nCAP signal relief Patch + standard of care) or control group (standard of care). Both the control group and intervention group will receive approved ERAS multimodal standard of care. Only the interventional group will receive an nCAP Signal Relief Patch.

Randomization will occur by assigning the participant a subject ID number, and this ID number will correspond to a treatment allocation based on a pre-designed randomization schema.

Subjects will undergo surgery using the approved ERAS anesthetic and post-operative pain management protocols.

After surgery, the subjects randomized to the intervention group will have the nCAP Signal Relief patch applied to their surgical dressing by a trained researcher in the immediate Post Anesthesia Care Unit (PACU). Subjects will be made aware at the time of consent and throughout the trial that they can drop out of the study at any time if they do not like wearing the nCAP Signal Relief Patch. The control group will not receive a patch but will receive the standard of care ERAS protocol. Subjects in the intervention group will be instructed to keep the nCAP Signal Relief Patch on their surgical dressing to avoid the risk for skin irritation.

Pain using a Numerical Rating Scale (NRS) at rest and with movement as well as opioid requirement will be assessed in the PACU and daily until discharge.

Subjects assigned to the intervention group should keep the nCAP Signal Relief Patch in place for 72 hours on their surgical dressing and they will be instructed to remove it at home.

Once the subject is discharged, they will be asked to complete a pain and opioid diary to record pain-related outcomes. They will be contacted via email (REDCAP survey) on post-operative day 1,2,3, 7, 14, and 30 to record postoperative opioid consumption, non-opioid consumption, NRS pain at rest and with movement, pain catastrophizing (via Pain Catastrophizing Scale) sleep quality (via PROMIS Sleep Disturbance Short Form 8a) and to assess functional recovery. Functional recovery will be assessed by determining the patient ability to walk 100 feet, go up 5 steps and raise their leg on postoperative days 1, 2, 3, 7, 14, and 30 as well as the pain associated with it. Patient satisfaction with pain management after surgery will be assessed at the 30 day follow up (0- least satisfied to 10-most satisfied). Subjects who are contacted via REDCap to complete follow-up questionnaires and do not complete them on the day they are assigned will be contacted via telephone for a reminder. They will be considered lost to follow up after 3 phone attempts.

Information will be collected from the medical record, including: patient demographics, medical history, medication summary while in the hospital, as well as progress notes from the entire encounter to determine the existence of adverse events.

Pre-and-Post Metric Evaluation

The use of a non-pharmacological nCAP Signal Relief Patch has the possibility of providing analgesia to post-surgical patients and reducing the number of opioids required following surgery. This will significantly impact patient outcomes, as patients will experience fewer opioid-related side effects (such as respiratory depression, post-operative nausea and vomiting, constipation, and delirium). This will also impact clinicians caring for post-operative patients, as there is the real potential they will have fewer conditions to monitor and treat as the patient recovers from surgery. The projected number of patients served by this project will initially be 70 enrolled participants at Shadyside Hospital, however, the data collected from this trial will serve countless patients and the community at large as physicians strive to move away from opioid use following surgery. Data collected from this pilot study will support a future proposal to the National Institute of Drug Abuse (NIDA) to fund a full-scale, randomized, placebo-controlled trial using the nCAP Signal Relief Patch.

Perhaps most importantly, the investigative use of the non-invasive nCAP Signal Relief patch has the ability to significantly decrease opioid requirement, postoperative pain, the hospital length of stay, the needs for opioid prescription following discharge from the hospital, improve early functional recovery, and increase patient satisfaction.

Being able to offer the orthopedic patients at UPMC Shadyside Hospital such an alternative might represent a non-pharmacological approach to pain management and an alternative to opioid, increase patient satisfaction, and improve early functional recovery.

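### The primary opioid count starts at patch placement, which controls never have, and no matching start is stated for them; a small bias is likely, and the repair is cheap

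*Protocol*

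**What the plan says.** **Start of the count.** Under Specific Aims, the primary aim concerns "reducing perioperative opioid requirement (up to 72 hours post-op"), followed at once by "Opioid requirement will be estimated following the placement of the patch". The start is therefore tied to placement and the end to surgery.

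**Data compared.** Study Design sets "Data collected following the placement in the treatment group" against the data obtained in the control group. Only the first side has a start. The same section calls the outcome postoperative opioid requirement, whereas the aim calls it perioperative.

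**What happens in each arm.** Under Data Collection and Outcome Measures, the patch is "applied to their surgical dressing by a trained researcher in the immediate Post Anesthesia Care Unit (PACU"). For the comparator, "The control group will not receive a patch but will receive the standard of care ERAS protocol". No sham is described. Pain scores "as well as opioid requirement will be assessed in the PACU and daily until discharge", a sentence that makes no distinction between arms. No maximum delay to placement is given.

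**SAP.** It lists total opioid consumption in OME mg with no start, end or window, and it asks for analysis by intention to treat.

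**The concern.** A randomised comparison of cumulative consumption needs the same clock in both arms. Here the start is an event that only one arm can have. Taken literally, a dose given after surgery but before placement is dropped for a patch patient, while no rule drops the same dose for a control. Part of any observed difference could then reflect how long each arm was counted.

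The direction is not fixed. If controls are counted from an earlier point, the patch is favoured; if from a later one, it is disfavoured. The trial is open label, so an undefined control start is also a choice that could be made with knowledge of the arm. A start that depends on receiving treatment also sits poorly with the SAP's intention-to-treat rule.

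**Working it through.** **1. Timing statements side by side**

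| Item | Patch arm | Control arm |
|---|---|---|
| Start (Specific Aims, Study Design) | Patch placement | Not stated |
| Setting (Data Collection) | PACU, then daily to discharge | PACU, then daily to discharge |
| End (Specific Aims) | 72 h post-op | 72 h post-op |
| Window in SAP | None | None |

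The end is common and the setting is shared. The undefined element is the control start.

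**2. Inputs for sizing**

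- From the documents: 30 per arm; alpha 0.05; a 72 h window; oxycodone doses of 5 and 10 mg, the 5 mg dose every 4 hours.
- Assumed, because the documents do not give them: a two-sided test; SD of 72 h OME of 40–60 mg; an oxycodone-to-OME factor of 1.5; steady use of 5–10 mg oxycodone per 4 h; a placement gap of 15–30 min as the reading closest to immediate placement, and 2 h as a stress case; no true effect.

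The SAP mentions a power calculation for 60 subjects but states no effect size, SD or power. It cannot be reproduced, and this point does not depend on it.

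**3. Shift in the mean**

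Hourly OME = 5 × 1.5 / 4 = 1.875 mg, up to 10 × 1.5 / 4 = 3.75 mg.

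- 15 min: 0.25 × 1.875 = 0.47 mg, up to 0.25 × 3.75 = 0.94 mg. Share of window: 0.25/72 = 0.35%.
- 30 min: 0.94 to 1.88 mg. Share: 0.5/72 = 0.69%.
- 2 h: 3.75 to 7.5 mg. Share: 2/72 = 2.8%.

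**4. Effect on the test**

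Noncentrality = shift / (SD × √(2/30)), df = 58, critical t = 2.0017. Error is the probability beyond either critical value. The favoured side is the patch if controls start earlier, and the controls if they start later; each side is nominally 2.5%.

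| Shift (mg) | SD 40: total (favoured / other) | SD 60: total (favoured / other) |
|---|---|---|
| 0.47 | 5.02% (2.77 / 2.25) | 5.01% (2.68 / 2.33) |
| 0.94 | 5.09% (3.07 / 2.02) | 5.04% (2.87 / 2.17) |
| 1.88 | 5.37% (3.74 / 1.62) | 5.16% (3.28 / 1.88) |
| 3.75 | 6.47% (5.45 / 1.02) | 5.65% (4.25 / 1.40) |
| 7.5 | 11.02% (10.64 / 0.37) | 7.64% (6.89 / 0.74) |

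A 15–30 min gap therefore gives 5.0–5.4%, and a 2 h gap gives 5.7–11.0%. An error of 10% needs a shift of 6.85 mg (SD 40) or 10.28 mg (SD 60). At 3.75 and 1.875 mg per hour that is 1.8–3.7 h and 2.7–5.5 h of delay.

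**5. Two checks on the steady-use assumption**

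- Lower use: the rates above imply 72 × 1.875 = 135 mg to 72 × 3.75 = 270 mg over the window. If mean use were instead 80 mg (assumed), the rate is 80/72 = 1.11 mg/h. A 30 min gap then shifts the mean by 0.56 mg, and the error at SD 40 is 5.03%.
- Front-loaded use: if a quarter of patients receive 15 mg OME before placement (assumed) and this is counted only in controls, the shift is 0.25 × 15 = 3.75 mg. The error is 6.5% (SD 40) or 5.7% (SD 60).

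Intraoperative opioid counted only in controls cannot be sized from the documents.

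**The case against.** The best defence is that the documents already imply a common start. Study Design speaks of postoperative requirement, the patch goes on in the immediate PACU, and opioid use is assessed in the PACU for everyone. The natural reading is PACU onward in both arms, so the mismatch is limited to doses between PACU arrival and placement. This stands as an argument about size. It does not supply the missing definition: a setting is not a time zero, no placement delay is stated, and the explicit placement rule applies to one arm only.

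Some stronger readings are tempting, but the documents do not carry them:

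- **That the result is materially biased towards the patch.** No passage says that controls start earlier, and a doubled error rate needs hours of delay, which is hard to square with immediate placement.
- **That a patient randomised to the patch who never has one placed has no endpoint.** This needs the most literal reading. The SAP requires intention to treat, opioid data are collected whatever happens with the patch, and no rate of non-placement is given.
- **That the second aim starts the clock for time to discharge at placement.** The wording "effects of nCAP Signal Relief Patch after the placement on postoperative pain" can simply describe the patch's effects.
- **That the 72 h end also fails after discharge.** "Once the subject is discharged, they will be asked to complete a pain and opioid diary to record pain-related outcomes", and no dose times are specified, but this is a separate matter that applies to both arms. A calendar-day cut-off would not be a safe repair: it could add up to 24 h of counting (24/72 = 33% of the window) and could act unequally if discharge times differ by arm.

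**Conclusion.** The definition gap is real: the primary count has a treatment-dependent start, no control start is stated, and the SAP gives no window. Its likely effect is small, at 5.0–5.4% two-sided error for a 15–30 minute gap, under the assumed SD, conversion factor and steady use. It becomes larger if placement is delayed (5.7–11.0% at 2 h), if PACU dosing is front-loaded (5.7–6.5% in the example), or if the word perioperative is taken to bring intraoperative opioid into the control count. Confidence is in the gap, not in the amount of bias. Severity is minor. It is still worth correcting because the text states an asymmetric rule for the primary endpoint and the repair is cheap.

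**What to change.** In both protocol and SAP, define the primary endpoint as total OME from one time zero that exists in both arms to 72 h after it, in all randomised patients, whether or when a patch is placed. PACU arrival and end of surgery both qualify. PACU arrival lies closer to placement, and end of surgery fits the existing post-op end; what matters is that one is chosen and written down. Report intraoperative opioid separately. Record the time of placement, and keep any post-placement count as a sensitivity analysis only.

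**Cost.** One definition in each document, and dose times from the hospital record, where the protocol at present names only a medication summary. Some early doses that the patch could not affect will be counted in both arms. If a quarter of each arm receives 15 mg before placement (assumed), the added variance is 15² × 0.25 × 0.75 = 42.2. The SD rises from 40 to 40.52, or from 60 to 60.35. At the differences that would have had 80% power (29.4 and 44.1 mg), power becomes 79.0% and 79.5%, a loss of about 0.5–1 point. Nothing in patient care changes.

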Study Title: A Pilot Study Investigating the nCAP Signal Relief Patch in Subjects Undergoing Primary Hip or Knee Replacement Surgery – A Pilot Trial

Principal Investigator: [name], PhD, MBA

IRB: STUDY22010018 NCT: 05252858

Statistical Analysis Plan Approval Date: 02/01/2022

Power calculation is for an anticipated 60 subjects who underwent TKA. Data is to be analyzed using intend-to-treat analysis plan. Data collection in this study includes the following measurements:

- Total opioid consumption (OME mg),
- Pain at rest and during movement rated on a standard Numerical Rating Scale (NRS, 0 = no pain and 10 = the worst pain imaginable),
- Area under the curve (AUC) for pain scores collected on POD 1, 2, 3, 7, 14, and 30,
- Time to discharge from the recovery room,
- Time to discharge from the hospital, and
- Overall subject satisfaction at the time of hospital discharge

The number of subjects requesting a prescription refill during the first 30-days post-operative will be calculated using the Pennsylvania Data Management Program.

Student's t-test, non-parametric Kruskal-Wallis test, or Pearson's chi-square test were used to determine differences in the distribution of continuous outcomes, and the chi-square test or exact test was used for differences in proportions for categorical outcomes between the treatment and placebo arms. Data will be presented as mean \pm standard deviation (SD) with a standard alpha set at 0.05.

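### Hip and knee patients are both enrolled, but joint is handled in neither the described allocation nor the SAP's unadjusted tests

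*Protocol*

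**What the plan says.** **Population.** The protocol's Inclusion Criteria admit patients "Scheduled for elective primary unilateral hip or knee replacement surgery". The title and the first Specific Aim also cover both joints. No quota or expected split is given. The operation is already scheduled at enrolment, so joint is known before randomisation.

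**Allocation.** The Randomization Process section says "Participating patients will be randomized by computer-generated random numbers to either the control group" or the intervention group. Data Collection and Outcome Measures adds that "subjects will be equally randomized to the intervention group" or control, and that "this ID number will correspond to a treatment allocation based on a pre-designed randomization schema". Treatment Groups gives 30 patients per arm. Neither document mentions strata, blocks or minimisation, and neither says that they are absent.

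**Analysis.** The SAP names Student's t-test, Kruskal-Wallis and chi-square or exact tests between two arms. It contains no covariate, joint term or stratified test. Its sizing statement reads "Power calculation is for an anticipated 60 subjects who underwent TKA", although the protocol enrols hips as well.

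**The concern.** Two different operations enter one comparison of 60 patients, and the primary outcome is opioid requirement up to 72 hours after surgery. If hip and knee patients differ in opioid need, two things follow.

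- A chance difference in joint mix between the arms moves the unadjusted treatment difference.
- Even with perfect balance, the spread between joints stays in the error term and widens the confidence interval.

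Either stratified allocation or a joint term would deal with the first. The second needs joint in the analysis. The documents describe neither. The protocol says that the pilot data will support a proposal for a full-scale trial, so a shifted or imprecise estimate would carry forward into that proposal.

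**Working it through.** **The plan's own figure.** The only relevant figure is 30 + 30 = 60. The SAP refers to a power calculation but gives no effect size, SD or power, so 60 cannot be reproduced.

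**Inputs from the documents.** Arms of 30 and 30 (Treatment Groups); both joints eligible (Inclusion Criteria); unadjusted tests and alpha 0.05 (SAP).

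**Assumptions, not in the documents.** K = 15 to 40 knees among 60; a hip-knee gap g of 0.25 to 1.0 within-joint SD in opioid use; a two-sided test; normal approximation for power.

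**Step 1: chance of a joint imbalance.** Fix the arms at exactly 30/30, the reading most favourable to the plan. Let x be the number of knees in one arm. Then x is hypergeometric (60 patients, K knees, 30 drawn), and the knee shares differ by |2x − K|/30. A gap of 20 points or more means |2x − K| ≥ 6.

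| Knees among 60 | Probability of a gap of 20 points or more |
|---|---|
| 15 | 7.2% |
| 20 | 17.0% |
| 30 | 19.6% |
| 40 | 17.0% |

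Every whole number of knees from 15 to 40 falls within 7.2% to 19.6%. When K is odd, 2x − K is odd, so the smallest qualifying gap is 7/30 (23 points); this is part of why the value at 15 is low. If allocation were simple randomisation instead, the range over the same mixes would be 8.7% to 15.5%.

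**Step 2: size of the shift.** Shift = imbalance × g. At 20 points:

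- g = 0.25: 0.20 × 0.25 = 0.05 SD
- g = 0.5: 0.20 × 0.5 = 0.10 SD
- g = 1.0: 0.20 × 1.0 = 0.20 SD

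The standard error of the difference, in within-joint SD, is √(2/30) = 0.258. The shifts are therefore 0.05/0.258 = 0.19, 0.10/0.258 = 0.39 and 0.20/0.258 = 0.77 of a standard error.

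**Step 3: precision lost by ignoring joint.** In a 50/50 mix the total SD is √(1 + g²/4). Power is Φ(δ/SE − 1.96), with SE = 0.258 × total SD. Take δ = 0.7236 SD, which gives 80.0% when between-joint variation is removed.

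| g | Total SD | Power, joint ignored |
|---|---|---|
| 0.25 | 1.008 | 79.4% |
| 0.5 | 1.031 | 77.6% |
| 0.75 | 1.068 | 74.7% |
| 1.0 | 1.118 | 70.8% |

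**Step 4: what a joint term costs.** With 18/30 knees in one arm and 12/30 in the other, the arm-joint correlation is 0.2. The variance inflation is 1/(1 − 0.04) = 1.04, about 2% on the standard error.

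**The case against.** **Two stronger readings.** A reader might infer that the list has no blocks and that the 30/30 split is left to chance. The documents do not support this. Computer-generated numbers are also how blocked lists are made, and equal randomisation, a schema prepared in advance and 30 per arm all fit a fixed or blocked list. The list type is simply not stated. The 10.3% chance of an exact 30/30 split, C(60,30)/2^60, would apply only to unrestricted allocation. Even then the harm is small: where 30/30 gives 80.0% power, 35/25 gives 78.9% and 38/22 gives 77.1%.

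A reader might also infer bias. That does not follow either. Over repeated randomisations the unadjusted test keeps its type I error, and chance imbalance in joint is part of the error that an unadjusted interval already covers. The shift in Step 2 should not be added on top of that interval.

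**Other objections.** The size rests on a hip-knee gap and a joint mix that the documents do not give, and even the largest shift shown is below one standard error. This stands, and it is why ranges are given. It can also be said that a prespecified joint term removes the shift from imbalance at almost no cost, so stratified allocation is largely a preference in a single-centre pilot. This stands too, but the SAP contains no such term. Finally, the SAP's sizing statement mentions knee replacement only. That would settle the matter only if hips were excluded, and the protocol includes them.

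**Conclusion.** The point holds in a limited form. Joint is known before randomisation, both joints are eligible, and the documents describe neither stratification by joint nor adjustment for it. This survives the reading most favourable to the plan, because equal arms do not balance the joints.

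Over the assumed mixes, roughly one trial in 14 to one in 5 would show a knee-share gap of 20 points or more. The resulting shift is 0.19 to 0.77 of a standard error, and the power lost is about 1 to 9 points, over the assumed gaps of 0.25 to 1.0 SD. At the low end the effect is negligible; at the high end it is worth preventing. The case for acting rests on the small cost of the remedy rather than on a demonstrated large effect. Nothing here shows that the list is unblocked, that arm sizes are left to chance, or that the comparison is biased.

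**What to change.** 1. **Analysis.** Prespecify joint (hip or knee) in the primary opioid analysis, as a term in a linear model or through a stratified rank test. If the list is already in use, this can still be done before the data are analysed.
2. **Allocation.** State the list type in the Randomization Process section. For allocations not yet made, generate permuted blocks within hip and knee strata. Vary the block sizes and conceal them from recruiting staff, because the trial is open label and the next allocation could otherwise be guessed.

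The two belong together: stratifying without a joint term balances the arms but leaves the precision loss of Step 3. The SAP's reference to knee replacement alone should be reconciled with the protocol's population at the same time.

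The cost is a short amendment to each document and two lists to manage instead of one. The joint term costs about 2% on the standard error at a 20-point imbalance, and less when the strata are balanced.

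### The SAP leaves out catastrophizing, sleep and function, although each is measured before randomization and again at follow-up; own-baseline adjustment would be a cheap gain in precision

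*Protocol*

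**What the plan says.** The protocol, under Data Collection and Outcome Measures, says of enrolled subjects that "they will be asked to complete the Pain Catastrophizing Scale (PCS"), together with PROMIS Depression and PROMIS Sleep Disturbance, before surgery. A baseline function test is done as well. Allocation comes afterwards: "Once these assessments are completed, subjects will be equally randomized to the intervention group". The baseline scores therefore cannot be affected by the patch.

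The same section repeats the measures on postoperative days 1, 2, 3, 7, 14 and 30, including "pain catastrophizing (via Pain Catastrophizing Scale) sleep quality (via PROMIS Sleep Disturbance Short Form 8a") and functional recovery (walking, steps, leg raise). Specific Aims places functional recovery in the secondary endpoint and lists sleep disorders among the opioid-related complications. PCS is not named there.

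The SAP's measurement list covers opioid consumption, NRS pain, pain AUC, two discharge times and satisfaction, and a further sentence adds prescription refills. PCS, sleep and function are absent. For continuous outcomes it names Student's t-test, the "non-parametric Kruskal-Wallis test" or Pearson's chi-square, and for categorical outcomes chi-square or an exact test. No covariate or regression model appears. The sample size is given as "Power calculation is for an anticipated 60 subjects who underwent TKA", and the protocol shows "Control Arm (n=30") and "Interventional Arm (n=30").

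**The concern.** For PCS and sleep the trial holds a pre-randomization value on the same scale as the follow-up value, and for function a closely related one. The plan makes no use of them. Either these outcomes have no planned analysis, or the SAP's general sentence on tests covers them and they would be compared without their baselines.

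What is at stake is precision. With 30 per arm and no stratification described, the chance difference in a baseline mean has a standard error of √(2/30) = 0.26 SD. It exceeds 0.3 SD in either direction in about 25% of such trials. An unadjusted follow-up comparison carries that difference in proportion to the baseline-outcome correlation. Its standard error already allows for this, so there is one loss here, of efficiency, and no added bias.

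There is also a specification issue. In an open-label trial, a covariate that is not named before the data are seen can be chosen afterwards. The protocol says the pilot is to support a proposal for a full-scale trial, and adjusted estimates with observed baseline-outcome correlations would help to size it.

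**Working it through.** **Inputs from the documents.** N = 60, 30 per arm, 1:1 allocation after the baseline assessments, alpha 0.05. The protocol's Pre-and-Post Metric Evaluation section also says the number "will initially be 70 enrolled participants at Shadyside Hospital"; the two figures are not reconciled, and 60 is used here.

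**Assumptions.** Two-sided testing, and baseline-outcome correlations r over a range, because the documents give none.

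**The plan's own figure.** The 60 cannot be reproduced, since no effect size, SD, power or sidedness is stated. What it implies can be computed: with 30 per arm, a two-sided t-test (58 df, noncentral t) has 80% power for a difference of 0.736 SD. That difference is the reference below.

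**Formula.** With k covariates that jointly explain a share R² of the within-arm variance, the variance of the adjusted effect relative to the unadjusted one is

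(1 − R²) × (1 + k/(N − k − 3)), with N − 2 − k degrees of freedom.

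The second factor is the cost of the covariates. Equivalent sample size is 60 divided by this ratio.

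**Own baseline, one covariate.** The cost factor is 1 + 1/56 = 1.018, and R² = r².

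| Assumed r | Variance ratio | Change in variance | Equivalent N | Power at 0.736 SD |
|---|---|---|---|---|
| 0 | 1.018 | +1.8% | 58.9 | 79.3% |
| 0.3 | 0.91 × 1.018 = 0.926 | −7% | 65 | 82.9% |
| 0.5 | 0.75 × 1.018 = 0.763 | −24% | 79 | 89.4% |
| 0.7 | 0.51 × 1.018 = 0.519 | −48% | 116 | 97.3% |

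Break-even is at r² = 1/57 = 0.0175, so r ≈ 0.13. These figures are for a continuous score such as PCS or sleep. They are only a guide for the three-level leg raise.

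**72-hour opioid use, two covariates (joint and PCS).** The cost factor is 1 + 2/55 = 1.036. Assume that joint explains nothing and that PCS has correlation r with opioid use.

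- r = 0.1: 0.99 × 1.036 = 1.026, power about 79%, a small loss.
- r = 0.2: 0.96 × 1.036 = 0.995, power 80.2% against 80.0% unadjusted, no practical gain.
- r = 0.4: 0.84 × 1.036 = 0.871, variance down 13%, power 85%.

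Break-even is at R² = 2/57 = 0.035, or r ≈ 0.19 from PCS alone.

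**Check of the formula.** A simulation with three covariates (4,000 trials per setting, normal data) gave variance ratios of 1.054, 0.856 and 0.734 at R² = 0, 0.2 and 0.3. The formula gives 1.056, 0.844 and 0.739.

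**If 70 is the analysed number.** One covariate then costs 1/66 = 1.5%, and r = 0.5 gives 0.75 × 1.015 = 0.761, still a 24% cut.

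**The case against.** The strongest reply is that nothing in the SAP is wrong. Under randomization the unadjusted tests are valid and the estimates unbiased, and a pilot may reasonably keep its analysis simple. That stands, and it limits the point to an improvement.

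Second, the SAP does not actually plan an unadjusted analysis of PCS, sleep or function; it does not list them. That also stands. For the outcomes it does list, no baseline value of the same measure is described: neither preoperative pain on the NRS nor a baseline of opioid requirement. The first defect is therefore the missing outcomes, and the adjustment belongs to the text that should be added for them.

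Third, a reader might infer that the plan is throwing away free precision, above all on the primary outcome. The documents do not support this. Each covariate has a cost, no correlation with opioid use is given, and the exclusion of active catastrophizing may narrow the spread of PCS and so weaken it as a predictor. At r = 0.2 the opioid model gains nothing if joint adds nothing.

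Fourth, a repeated instrument does not guarantee a high correlation. The larger gains need r of 0.5 to 0.7, which is assumed. For function the match is looser: baseline is a test the subject performs, while after discharge the information comes by emailed survey with telephone reminders, and leg raise has only three levels.

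What survives is that one own-baseline covariate risks about 2% in variance and gains at any correlation above about 0.13.

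**Conclusion.** The point holds as a cheap improvement. Function and sleep belong to the secondary endpoint, PCS is collected at every follow-up, and all three have pre-randomization measurements, yet the SAP neither lists them nor plans any baseline-adjusted analysis.

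For PCS and sleep the net cut in variance runs from about 7% to 48% across assumed correlations of 0.3 to 0.7. Those figures rest on N = 60 with complete data, a roughly linear relation and those assumed correlations. For function the direction is the same but the size is less certain, and it also depends on the baseline test recording the items that are followed up. For 72-hour opioid use the gain is anywhere from about nil to modest. It would be wrong to conclude that the planned tests are invalid or biased.

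**What to change.** In the SAP:

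1. Add follow-up PCS, PROMIS Sleep Disturbance and function to the measurement list, and say which visit or visits are compared.
2. Analyse PCS and sleep by ANCOVA with arm and the measure's own baseline. Analyse leg raise (0 to 2) by an ordinal model with arm and baseline leg raise.
3. Keep the unadjusted test of each as a sensitivity analysis.
4. State a rule for missing baseline forms.
5. Optionally, prespecify a model for 72-hour opioid use with arm, joint (hip or knee) and baseline PCS. Fix the outcome scale in advance, and choose one that allows zero use: the pain protocol under Study Design gives only non-opioid drugs at low scores, so zeros are possible and a plain log would fail. A rule to take logs only if the data look skewed would leave the choice open until after the data are seen.

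The cost is SAP wording and one degree of freedom per own-baseline covariate (two for the optional model). No new data are needed.
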